1.2 Rationale & Purpose

Our proposed implementation research is designed to evaluate a novel approach to engage individuals with HIV who are at the highest risk for not accessing care or adhering to treatment. We are not testing CAB-RPV LA; this is an approved drug. We are also not studying the drug nor are we studying it for a new population, new dosage or new route of administration. Rather, we are conducting an implementation study and propose to test implementation CAB-RPV LA in community-based settings.

Strategies to implement evidence-based interventions to end the HIV epidemic are urgently needed. Despite highly effective antiretroviral treatment (ART) for HIV infection and multiple effective prevention interventions, there are approximately 40,000 new HIV infections annually in the US (CDC, 2019). Two of the four pillars of the US Department of Health and Human Services "Ending the HIV Epidemic" initiative are to:

Protocol Title: **CAB-RPV LA Implementation Strategies for High-Risk Populations**

1) treat individuals with HIV rapidly and effectively to achieve viral suppression; and 2) prevent new infections by using evidence-based interventions (<https://www.cdc.gov/endHIV/>).

Our implementation research addresses three ViiV Healthcare priority areas: 1) implementation of CAB-RPV LA delivery models in non-HIV clinic settings; 2) feasibility and acceptability of bringing CAB-RPV LA injections to the patient (rather than bringing the patient to the medication in more traditional ways only); and 3) addressing challenges of CAB-RPV LA delivery amongst high risk populations, specifically women and men of color, immigrants, homeless individuals, active substance users, transactional sex workers, individuals released from incarceration, and individuals who have fallen out of HIV care. Our study (which overall incorporates three Objectives) addresses the following research questions:

A. Implementation Questions

1. Will community-based delivery of CAB-RPV LA be an acceptable and feasible delivery method to high-risk PLWH from the patient, provider and community organization perspectives? (acceptability/feasibility)
2. Can a community-based delivery strategy lead to initiation and completion of injections for six months for at least 80% of individuals who are enrolled into Cohort 1 for an initial visit in an outreach setting? (reach)

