See Section 11 for information on the details of the sample size calculations and Section 7.2 for how study staff will stay in contact with participants to maximize potential for longer term engagement.
3. What are the characteristics of patients who are most likely to have an initial injection and do these characteristics differ for individuals who receive CAB-RPV LA in and outside of the HIV clinic? (equity)
4. Are patients who are seen for CAB-RPV LA in community-based settings satisfied with their HIV care? (patient-centeredness)
5. Will consistent delivery of CAB-RPV LA be possible in community-based (non-HIV clinic) settings? (feasibility)
6. Will the providers at a drop-in center or community-based organization be willing to implement CAB-RPV LA within their non-traditional setting? (adoption)

B. Clinical Questions

1. Can individuals targeted for intervention at community-based delivery site achieve viral suppression and receive initial injection?
2. Can a community-based delivery strategy ensure engagement in services and receipt of CAB-RPV LA visits among high-risk populations? (effectiveness)
3. Is a community-based delivery strategy using CAB-RPV LA superior to the current standard of care in ensuring treatment adherence for individuals at highest risk? (effectiveness) Can high-risk individuals who receive community-based CAB-RPV LA be adherent to care, defined as undetectable viral load, for six months?

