11.0 Statistical Plan

11.1 Study Hypotheses

Objective 2 has the following hypotheses:

- **H1:** Changing the service site will result in $\geq 80\%$ of participants in the community-based intervention arm beginning injections
- **H2:** Of participants in the community-based intervention arm who begin injections, 80% will complete 6 injections
- **H3:** Changing the service site will result in improved engagement in care for participants in the community-based intervention arm compared to matched controls (Cohort 3) at 6 months for intervention patients compared to control group patients
- **H4:** Changing the service site will result in superior HIV viral suppression at 6 months compared to for participants in the community-based intervention arm compared to matched controls (Cohort 3)
- **H5:** Participants in the community-based intervention arm will be equally satisfied with their care compared to patients who receive care in clinic settings (Cohort 2).

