11.2 Sample Size Calculation

For the pilot study, we have powered our study to address hypothesis 4 above. Our power calculation is as follows: With a total of 60 participants, 20 patients in each cohort, the study will have the statistical power to detect clinically meaningful differences in both engagement in care (appointment adherence) and undetectable viral load at 6 months. Depending on appointment adherence and undetectable viral load in the standard of care control group, we will be able to detect a minimum 40% difference, assuming 80% power and type 1 error probability (alpha) = 0.05. Estimates from our study sites suggest that undetectable viral load can be as low as 50% at any given time in our high-risk population. If we observe this level in the standard of care control group at 6 months, we will be able to observe a difference of 40% (or 90% vs. 50%) between the Cohort 1 CAB-RPV LA in the CBOc arm vs. the Cohort 2 CAB-RPV LA in the clinic arm and Cohort 1 CAB-RPV LA in the CBO arm vs. Cohort 3 no CAB-RPV LA arm participants, respectively. Because our intention to treat (ITT) analytic approach may mean an even lower proportion in controls (because missing data will be considered detectable), we believe our sample size is sufficient to yield rigorous clinical outcomes.

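### The reach question sets 80% of all enrolled in Cohort 1 as its target, but H1 and H2 can both be met with 65% of them completing, and completion is defined in two ways

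*Combined protocol and SAP*

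**What the plan says.** Section 1.2, implementation question 2, labelled reach, sets one combined target: "initiation and completion of injections for six months for at least 80% of individuals who are enrolled into Cohort 1". The denominator is everyone enrolled in Cohort 1, and the event is starting and then completing six months of injections. The text directly after it adds "See Section 11 for information on the details of the sample size calculations".

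Section 11.1 has no hypothesis in that form. H1 concerns 80% or more "of participants in the community-based intervention arm beginning injections". H2 reads "Of participants in the community-based intervention arm who begin injections, 80% will complete 6 injections". H2 counts only starters in its denominator, and its event is a number of injections, not a period.

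Section 11.2 fixes the size: "With a total of 60 participants, 20 patients in each cohort". It says "we have powered our study to address hypothesis 4 above", which is viral suppression, and it also mentions engagement in care. Section 11.3 describes models for engagement and viral load. Neither section gives an analysis, an interval or a rule for H1, H2 or the reach question.

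Sections 7.1 and 7.6 let a Cohort 1 participant move to injections every other month after the second injection.

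**The concern.** A question and the hypotheses that serve it should give the same answer on the same data. Here the question applies 80% once, to everyone enrolled, while the hypotheses apply 80% twice, the second time to a smaller group. A result could therefore be reported as meeting both hypotheses while the trial's own reach question is answered no.

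The two descriptions of completion add a second mismatch. A participant who receives every injection due on the every-other-month schedule would count as a success for the question and a failure for H2.

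The purpose of this pilot is to learn whether delivery outside the HIV clinic is feasible. If the documents support two different verdicts on reach, the choice between them could be made after the data are seen.

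**Working it through.** **The plan's own figure.** Section 11.2 gives 20 per cohort for 90% against 50%, "assuming 80% power and type 1 error probability (alpha) = 0.05". Two-sided, without continuity correction:

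n = [1.960 × √(2 × 0.70 × 0.30) + 0.842 × √(0.90 × 0.10 + 0.50 × 0.50)]² / 0.40² = (1.270 + 0.491)² / 0.16 = 19.4, rounded up to 20 (power at 20 per cohort: 81.3%).

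The stated size reproduces. It concerns H4 and is not affected by this point.

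**Inputs for reach.** Cohort 1 has 20 people (Section 11.2). Reach needs at least 80% of enrolled to start and complete (Section 1.2), which is 16 of 20. H1 needs at least 80% to start (Section 11.1), also 16 of 20. H2 needs 80% of starters to complete, read here as at least 80%. Steps 1 to 3 treat completion as the same event in the question and in H2.

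**Step 1: thresholds.** 0.80 × 0.80 = 0.64 of enrolled. If exactly 80% start, the question is met only if every starter completes (0.80 / 0.80 = 100%). With equal rates at both steps, each must be √0.80 = 89.4%.

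**Step 2: whole people.** Fewest completers that satisfy H1 and H2:

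| Starters of 20 | Fewest completers for H2 | Share of enrolled | Reach question (16/20) |
|---|---|---|---|
| 16 | 13 (81.3% of starters) | 65% | missed |
| 17 | 14 (82.4%) | 70% | missed |
| 18 | 15 (83.3%) | 75% | missed |
| 19 | 16 (84.2%) | 80% | met |
| 20 | 16 (80.0%) | 80% | met |

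Six (starters, completers) results meet both hypotheses and miss the question: (16,13), (16,14), (16,15), (17,14), (17,15) and (18,15). The reverse cannot happen under one definition: 16 completers imply at least 16 starters, and 16 out of at most 20 starters is at least 80%.

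Exact (Clopper-Pearson) 95% intervals: 13/20 gives 41-85%; 16/20 gives 56-94%.

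**Step 3: how often they would conflict.** Starters are binomial with n = 20 and rate p1; completers are binomial among starters with rate p2. Each target is judged by the observed proportion. The documents give no expected rates and no such pass rule, so both are assumptions.

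| Assumed p1 / p2 | H1 and H2 both met | Reach met | H1 and H2 met, reach missed |
|---|---|---|---|
| 80% / 80% | 34.5% | 10.1% | 24% |
| 90% / 85% | 71% | 48% | 23% |
| 95% / 90% | 91% | 85% | 7% |
| 100% / any | – | – | 0% |

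**Step 4: the completion definitions.** Cohort 1 injections scheduled through month 7 in the Section 7.0 regimen table:

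- Every other month, with oral lead-in: months 2, 3, 5, 7 = 4.
- Every other month, no lead-in: months 1, 2, 4, 6 = 4.
- Monthly, with lead-in: months 2 to 7 = 6.
- Monthly, no lead-in: months 1 to 7 = 7.

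A participant on the every-other-month schedule who misses nothing meets the question's wording and cannot meet H2's. If enough people choose that schedule, the question can be met while H2 fails, so the one-directional result in Step 2 no longer holds.

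**The case against.** The strongest reply is that 65% is a floor. With 19 or 20 starters, meeting H2 also meets the reach question. Sections 5.2 and 7.1 already exclude people who are unwilling to take the injections or unable to complete eligibility testing, so near-complete starting is plausible. This stands and limits the size of the point. It does not remove it: Section 7.1 rules out an injection on the day of enrollment, so people can still be lost between enrolling and starting.

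Several stronger readings are tempting and are not supported:

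- A reader might infer that meeting H1 and H2 means about 64-65% complete. That is only the lowest passing result.
- A reader might infer that reach is the main outcome, or that a go/no-go decision rests on a bare 80%. Reach is one of six implementation questions. None is called main, no decision rule is stated, and nothing says H1 or H2 will be judged by a point estimate alone.
- A reader might take the pointer to Section 11 as a promise of a sample size for reach. It refers only to the sample size calculations in general; Section 11.2 supplies one and openly names H4 as its basis.
- A reader might call this a miscalculation. No stated figure is wrong; two statements of a target disagree.

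It can also be said that nothing shows the question, and not H1 and H2, to be the intended target. That is fair, and either could be aligned to the other.

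**Conclusion.** The concern holds as an internal inconsistency of moderate size. With 20 enrolled and one meaning of completion, H1 and H2 can be met at 13/20 (65%) while the reach question needs 16/20, and only when 16 to 18 people start. The chance of that conflict runs from about 24% to zero across the assumed rates; it depends mainly on how many enrolled people start, which the documents do not predict.

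Separately, and without any assumed rate, H2 as worded counts fully adherent every-other-month participants as non-completers, so the disagreement can go in either direction. No other section reconciles the two targets. The arithmetic of thresholds and counts is certain; the conflict probabilities are illustrative.

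**What to change.** State one reach outcome in Sections 1.2 and 11.1: the proportion of all enrolled Cohort 1 participants who start and receive every injection due on their own assigned schedule over the six-month period. Say which study months that period covers, because a monthly participant who takes the oral lead-in has a sixth scheduled injection only in month 7. Keep the 80% benchmark (16/20) and add to Section 11.3 that the proportion will be reported with an exact 95% CI. Retain the H1 and H2 proportions as descriptive components, using the same completion definition.

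If the sponsor intends H1 and H2 as the target, reword the reach question to match them, state that they imply as little as 64% of enrolled completing, and still adopt one definition of completion.

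The first option makes the target harder to meet than H1 and H2 do; the second openly accepts a lower one. Either is a change of wording and reporting. Section 10.1 already has injections recorded in the EHR, so no new data or participants are needed, and no dose or schedule changes.

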4.0 Potential Risks & Benefits

4.1 Potential Risks

The primary risk related to participation in the study is dropping out of care and not being linked to care. However, it is important to note that this is an ongoing risk for these patients in general given their social determinants of health putting them at higher risk of not being engaged in their care. There are risks related to the medication itself, which include injection site reactions, pyrexia, fatigue, headache, musculoskeletal pain, nausea, sleep disorders, dizziness, rash, diarrhea, pain/discomfort, nodules, induration, swelling, erythema, pruritus, bruising/discoloration, warmth and hematoma. Less common risks include gastrointestinal disorders, hepatobiliary disorders, weight increase, psychiatric disorders including anxiety (irritability, depression, abnormal dreams) and skin hypersensitivity. There is also the risk that if a participant is non-adherent to the injections, they may become resistant to cabotegravir and rilpivirine.

Special attention will be given to any medical issues related to the injections, including perceived soreness, fatigue, and other unintended consequences throughout the trial and standard referral to BMC will be made in such cases. It is important to note that CAB-RPV LA has been fully approved for use; the question for this study is NOT the effectiveness of the medication, but rather whether it can be delivered in non-traditional settings. Consent procedures will include detailed discussion of what the use of CAB-RPV LA will entail, both advantages and disadvantages, and an opportunity for the potential participant to ask questions. Once consent for screening has been provided,

Protocol Title: **CAB-RPV LA Implementation Strategies for High-Risk Populations**

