5.0 Study Subject Selection

5.1 Subject Inclusion Criteria

Cohort 1: Age \geq 18 years, English or Spanish speaking, HIV-positive, labs indicate that they are a candidate for the medication and virally suppressed, meaning that their HIV-1 ribonucleic acid is less than 50 copies per mL. Individuals enrolled in Cohort 1 must be willing to complete the locator form (Appendix G) in order to receive appointment reminders prior to their monthly/bi-monthly injection and ongoing follow-up by outreach and study staff to maximize potential for adherence.

Cohort 2: Currently enrolled in care at CID and receiving CAB-RPV LA injection, age \geq 18 years, English or Spanish speaking. Individuals enrolled must be willing to complete the locator form in order to receive appointment reminders prior to follow-up data collection.

Cohort 3: Enrolled in care at CID but not receiving CAB-RPV LA, age \geq 18 years, matched to participants demographically and in terms of other characteristics in Cohort 1 at a 1:1 ratio. Individuals in Cohort 3 will be receiving the Standard Care for HIV treatment in CID. Standard of care for this group includes access to regular appointments with their HIV provider, oral ART, case management services, etc. Individuals enrolled must be willing to complete the locator form in order to receive appointment reminders prior to follow-up data collection.

Our goal for all three cohorts is to enroll a percentage of women that is equivalent to the number of female patients served by the sites, approximately 20-30% female. Similarly, we will ensure that our sample includes individuals of color proportional to their representation within the setting across all three cohorts.

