6.0 Study Intervention

The study intervention for Cohort 1 is delivery of HIV medication at Project Trust, rather than in the BMC HIV Clinic. Project Trust (PT) is a street-based drop-in clinic that is focused on STD testing, treatment, harm reduction, and social services engagement. PT engages in outreach work, provides individuals with substance use disorder safe injection kits, and is a well-established community site for the target population frequenting the area, which is home to a high number of individuals who are homeless, diagnosed with substance use disorder, and are living with HIV. Study staff who will be administering the injection are all trained clinicians (either nurse practitioners or physicians) and are BMC staff. Individuals administering the injection will all be listed on the BUMC Internal Review Board study protocol.

There is not a clinical intervention or any intervention beyond data collection for Cohorts 2 or Cohort 3. Cohort 2 will be receiving their CAB-RPV LA within the BMC HIV clinic as their standard care. Cohort 3 will be receiving standard of care (not CAB-RPV LA) and will be patients of the BMC HIV clinic. Individuals enrolled in all three cohorts will be asked to complete a survey at study enrollment (baseline), between 2-4 months after their enrollment (midpoint) and a final follow up between 6 - 8 months post baseline. Clinical data will be obtained from the BMC EHR via the clinical data warehouse at these time periods and no other data will be collected directly from study participants for Objective 2.

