7.7 Missed Injection Target Dose Timeline

Protocol Title: **CAB-RPV LA Implementation Strategies for High-Risk Populations**

In order to ensure that patients receive their injection within the 7 days of their target injection date, the following outline will be followed. This outline is applicable for any missed dose:

- **Day 1 Post Target:** The study team will outreach to the participant via their preferred communication method as specified in their locator form in order to encourage them to return within the following three days. The encounter will be tracked in the study Log Book.
- **Day 3 Post Target:** The study team will outreach again to the participant via the preferred communication method to encourage them to return the following day. The encounter will be tracked in the study Log Book.
- **Days 5-7 Post Target:** The study team will enlist BMC's ARCH and PT street-based outreach workers who are experienced with and successful at reaching and engaging high-risk patients. The outreach workers will conduct active outreach to the participant in the community to bring them in for a visit. If active outreach is unsuccessful, the study team will also use the contacts on the locator form to attempt to reach the participant. The encounter will be tracked in the study Log Book.
- **Upon Return Within 14 Days Post Target:** The study clinician will obtain a viral load and genotype. If the participant's viral load is less than 200 copies per mL, they will administer the CAB-RPV LA. If the participant's viral load is over 200 copies per mL, the study clinician will refer them to their primary care provider who will make the determination about whether or not an injection is appropriate. The encounter will be tracked in the study Log Book.
- **If participant returns after 15 days Post Target:**
 - **Missed Dose Occurs within 2 months of Initiation Injection:** The participant will be given a maintenance dose at their next contact with study staff (400mg/600mg 2 ml). The participant will then resume their normally scheduled injection plan, i.e. next injection scheduled to be given 25-32 days after maintenance dose administered.
 - **Missed Dose Occurs after first 2 months of injection:** The participant will be given a loading dose instead of their scheduled dosing amount (600mg/900 mg 3 ml). The participant will then resume their normally scheduled injection plan.

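### H3 and H4 credit the service site with a Cohort 1 versus Cohort 3 difference that also contains drug, outreach and entry viral suppression

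*Combined protocol and SAP*

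**What the plan says.** Section 11.1 states H4 as "Changing the service site will result in superior HIV viral suppression at 6 months", comparing the community arm with the matched controls in Cohort 3. H3 uses the same cause and the same comparator for engagement in care. Section 11.2 says the study is powered for H4.

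The declared intervention is the place of delivery. Section 6.0: "The study intervention for Cohort 1 is delivery of HIV medication at Project Trust, rather than in the BMC HIV Clinic". Section 4.1 adds that "the question for this study is NOT the effectiveness of the medication, but rather whether it can be delivered in non-traditional settings".

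The comparator differs in drug as well as place. Section 6.0: "Cohort 3 will be receiving standard of care (not CAB-RPV LA) and will be patients of the BMC HIV clinic". Section 5.1: "Standard of care for this group includes access to regular appointments with their HIV provider, oral ART, case management services, etc".

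Contact with study staff also differs. Section 7.1 gives Cohort 1 a study contact one week and one day before each injection. Section 7.7 sets out stepped missed-injection follow-up, and by days 5 to 7 "The outreach workers will conduct active outreach to the participant in the community to bring them in for a visit". For Cohorts 2 and 3, Section 5.1 ties reminders to data collection: "Individuals enrolled must be willing to complete the locator form in order to receive appointment reminders prior to follow-up data collection".

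Entry rules differ too. Sections 5.1 and 5.2 require viral suppression before CAB-RPV LA and exempt Cohort 3. Section 7.2 matches Cohort 3 to Cohort 1 on drug use history, housing status and sex, not on viral load.

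**The concern.** The hypotheses name one cause, the site. The contrast chosen to test them changes several things at once. A positive H3 or H4 would be consistent with a benefit from the site, the injectable regimen, the reminders and outreach, a better starting position on the outcome itself, or any mixture of these. The stated conclusion would then go beyond what the comparison identifies, and for H4 that is the conclusion the sample size was built around.

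The protocol already holds a question that this contrast is closer to answering. Clinical question B3 in Section 1.2 asks whether community delivery with CAB-RPV LA beats current standard care for adherence. H3 and H4 are not worded that way.

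**Working it through.** **1. What differs between the cohorts**

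| Feature | Cohort 1 | Cohort 2 | Cohort 3 |
|---|---|---|---|
| Site (6.0) | Project Trust | HIV clinic | HIV clinic |
| Regimen (5.1, 6.0, 7.0) | CAB-RPV LA, being started | CAB-RPV LA, already being received | Oral ART |
| Study reminders (5.1, 7.1, 7.3) | Before every injection, and for data collection | For data collection, timed to injections where possible | For data collection |
| Study missed-injection outreach (7.7) | Yes | Not described | Not applicable |
| Suppressed at entry (5.1, 5.2) | Required | Required before starting CAB-RPV LA | Not required |
| Matched to Cohort 1 (7.2) | – | No | Drug use, housing, sex |

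Section 11.3 represents cohort by a single dummy variable. All of Cohort 1 is assigned the injectable with study outreach and none of Cohort 3 is. No covariate can separate site from components that coincide completely with cohort.

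**2. The plan's own figure**

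Inputs from Section 11.2: 90% versus 50%, 80% power, alpha 0.05, 20 per cohort. Sidedness is not stated; two-sided is assumed. With pooled proportion 0.70:

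n = [1.96·√(2·0.7·0.3) + 0.84·√(0.9·0.1 + 0.5·0.5)]² / 0.40² = (1.270 + 0.491)² / 0.16 = 19.4, rounded up to 20.

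Power at n = 20 is Φ[(0.40 − 0.284)/0.130] = Φ(0.889) = 81.3%. The figure reproduces, so the arithmetic is sound for a 90% versus 50% contrast. The question is what that contrast identifies.

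**3. H4 with no site effect**

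Assume the site adds nothing, Cohort 3 is at 50%, and the non-site differences together raise Cohort 1 by r. With p̄ = 0.5 + r/2:

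P(significant) ≈ Φ{[r − 1.96·√(2p̄(1−p̄)/20)] / √[(p₁(1−p₁) + 0.25)/20]}, where p₁ = 0.5 + r.

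| Non-site gain r | Standardised value | Pooled normal | Fisher's exact test |
|---|---|---|---|
| 10 points | (0.10 − 0.308)/0.157 = −1.33 | 9% | 5% |
| 20 points | (0.20 − 0.304)/0.152 = −0.68 | 25% | 16% |
| 30 points | (0.30 − 0.296)/0.143 = 0.03 | 51% | 41% |
| 40 points | (0.40 − 0.284)/0.130 = 0.89 | 81% | 74% |

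These are unadjusted approximations; Section 11.3 plans multivariable logistic regression. The values of r are assumptions, because nothing in the documents divides the expected effect among its parts.

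**4. What Cohort 1 versus Cohort 2 can show**

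This contrast holds the drug constant. If both cohorts are at 90% (18 of 20), the Wald 95% half-width is 1.96·√(2·0.9·0.1/20) = 0.186, about ±19 points. The Newcombe interval uses Wilson limits of 0.699 and 0.972 for 18/20: √(0.201² + 0.072²) = 0.214, about ±21 points. With Cohort 1 at 90%, power is 81%, 60%, 35% or 14% if Cohort 2 is at 50%, 60%, 70% or 80% (Cohort 2 rates assumed). Section 11.2 applies 90% versus 50% to this contrast as well, although it describes the 50% as a standard-of-care rate.

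Section 11.3 names the Cohort 1 versus Cohort 2 model for engagement. For viral load it says only that a similar model will be used, without naming contrasts.

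**5. Entry suppression**

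Everyone in Cohort 1 starts below 50 copies/mL; Cohort 3 members may start above it. Because no one in Cohort 1 is unsuppressed at entry, unsuppressed Cohort 3 members have no counterpart. Adjusting for a yes/no baseline indicator therefore leaves the comparison resting on the suppressed Cohort 3 members.

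**The case against.** The strongest reply is that the package is in plain view. The protocol summary lists three arms, including standard care. B3 asks the package question, and Section 11.2 labels Cohort 3 as receiving no CAB-RPV LA. Section 3.0 describes the strategy as a change of delivery site to a community-based clinical intervention, so the wording of H3 and H4 can be read as shorthand. This is also a pilot. All of that is fair, and it shows that the repair is mainly one of wording. It does not rescue the hypotheses: Section 6.0 defines the intervention as the site alone, Section 4.1 sets drug effectiveness aside, and small size does not make an unidentified cause identifiable.

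The outreach contrast may be smaller than it looks. Section 7.3 schedules data collection for Cohorts 1 and 2 to fall on injection visits where possible, with contacts a week and a day before, so Cohort 2 may get study reminders around some injections. The ARCH outreach workers belong to BMC, and Cohort 3's usual care includes case management. The documents do not say how much outreach Cohort 3 would get as usual care. That point stands, but the drug difference remains whatever the answer.

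The 81% at a 40-point non-site gain is the plan's own power with the whole gap assigned to non-site causes. That is correct, which is why the range is shown and not that figure alone.

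**Conclusion.** H3 and H4 state a conclusion about site that Cohort 1 versus Cohort 3 cannot support. The contrast addresses at most B3, and for viral load even the package reading is confounded by entry suppression. With no site effect, H4 would be declared in roughly 9% to 81% of trials as the assumed non-site gain runs from 10 to 40 points (pooled normal, two-sided, 20 per cohort, 50% in Cohort 3). This rests on the cohort definitions in the protocol; only the size of the illustration rests on assumed splits.

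Three stronger readings are tempting and not supported:

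- A reader might infer that a positive H4 is most likely not a site effect. The documents do not divide the effect, so no such probability follows.
- A reader might infer that only Cohort 1 gets study reminders near injections. Section 7.3 leaves room for some in Cohort 2.
- A reader might infer that Cohort 1 versus Cohort 2 isolates site plus outreach. Cohort 2 is unmatched and already receiving injections at entry, so treatment stage and selection enter as well.

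**What to change.** 1. Reword H3 and H4 as community-delivered CAB-RPV LA with outreach, compared with standard clinic-based care, in line with B3.
2. State that only Cohort 1 versus Cohort 2 informs the site question. Specify that contrast for viral load as well as engagement, and report it as a difference with a 95% CI. State that it also reflects study outreach, an unmatched comparator, and patients already receiving injections at entry, and that it will be imprecise at 20 per cohort.
3. State that Cohort 1 versus Cohort 3 is also confounded by entry suppression. Report H4 accounting for baseline viral load, for example among Cohort 3 members suppressed at baseline. Section 7.3 already collects viral load from the EHR at enrolment.

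No new participants or data are needed. The cost is a narrower claim from H3 and H4. Item 3 also leaves fewer controls: if half of Cohort 3 were suppressed at entry (an assumption that borrows the 50% in Section 11.2), 10 of 20 would remain.
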